### 11.1.2 Cycle Delays

Table 11.1.2.1 Summary of luteinizing hormone-releasing hormone agonist dose delays

**Table 11.1.2.2 Length of delay**

†† Denominator = Number of cycles susceptible to have dose delay  
 Part A, patients assigned to Sequence 1; Part B, sequence assigned randomly.  
 S1, Sequence 1; S2, Sequence 2; TR, test-reference; RT, reference-test.

### Listing 11.1.2.3 Dose delays

Study Part	Sequence	Treatment Group*	Subject	Cycle	Delay (days)	Reason for delay
...						
		* ITZ+LRB / LRB				

\* ITZ+LRB / LRB

### 11.1.3 Dose Reductions

Table 11.1.3.1 Summary of lurtinectedin dose reductions

† Excluding patients who received only the first cycle.

‡ Related or unknown relationship

†† All cycles excluding first cycle

\*\* Denominations

### Denominator

### Part A, patients as

## SI, Sequence

### Listing 11.1.3.2 Dose reductions

Study Part	Sequence	Treatment Group*	Subject	Cycle	Lurbinectedin intended dose (mg/m  )	Reason for dose reduction	Specify
...							

---

\* ITZ+LRB / LRB

#### **11.1.4 Any Other Dose Modifications**

##### **Listing 11.1.4.1 Dose interruptions for lurtinectedin**

Study Part	Sequence	Treatment Group*	Subject	Cycle	Date	Reason for interruption	Specify
...							

\* ITZ+LRB / LRB

##### **Listing 11.1.4.2 Dose Omissions for lurtinectedin**

Study Part	Sequence	Treatment Group*	Subject	Cycle	Date	Reason for omission	Specify
...							

\* ITZ+LRB / LRB

##### **Listing 11.1.4.3 Dose not taken according to protocol for Itraconazole**

Study Part	Sequence	Treatment Group*	Subject	Cycle	Date	Reason for omission	Specify
...							

\* ITZ+LRB / LRB

## 11.2 Adverse Events (AEs)

This analysis will be carried out on evaluable patients for the safety population.

All adverse events tables will be listed by study part and sequence and differentiating by treatment (Test, Reference or both). Additional groups could be done (such as PM01183 alone or in combination) if required, and a sequential number will be added at the end of the table number.

AEs consisting of laboratory abnormalities (e.g., neutropenia) may be under-reported as AEs. Since these events are better evaluated using objective laboratory results, laboratory abnormalities will be discussed in Section 11.4.

The type of toxicity and worst grade or severity by cycle and by patient will be summarized according to System Organ Class (SOC) and Preferred Term (PT) as per the MedDRA dictionary. Subsequent grouping of similar or clinically related items might be appropriate at the time of the analysis. Tables will be organized by category of events using SOC and PT. Grades could be presented by separate or any other grouping at the time of the analysis.

### 11.2.1 Display of Adverse Events

Table 11.2.1.1 Summary of adverse events

	Part A			Part B		
	S1		S1		S2	
	T	R	T	R	R	T
	N(%)	N(%)	N(%)	N(%)	N(%)	N(%)
No. of patients with any AE						
No. of patients with any treatment-related † AE						
Patients with any grade 3/4 AE						
Patients with any grade 4 AE						
No. of patients with any grade 3/4 treatment-related † AE						
No. of patients with any grade 4 treatment-related † AE						
No. of patients with any SAE						
No. of patients with any treatment-related † SAE						
No. of patients with any grade 3/4 SAE						
No. of patients with any grade 4 SAE						
Any grade 3/4 treatment-related † SAE						
Any grade 4 treatment-related † SAE						
No. of patients with deaths associated with AEs						
No. of patients with deaths associated with treatment-related † AEs						
No. of patients with dose delays associated with AEs						
No. of patients with dose delays associated with treatment-related † AEs						
No. of patients with dose reductions associated with AEs						
No. of patients with dose reductions associated with treatment-related † AEs						
No. of patients with dose interruptions associated with AEs						
No. of patients with dose interruptions associated with treatment-related † AEs						

	Part A+B		Total	
	S1			
	T	R		
	N(%)	N(%)	N(%)	
No. of patients with any AE				
No. of patients with any treatment-related † AE				
Patients with any grade 3/4 AE				
Patients with any grade 4 AE				
No. of patients with any grade 3/4 treatment-related † AE				
No. of patients with any grade 4 treatment-related † AE				
No. of patients with any SAE				
No. of patients with any treatment-related † SAE				
No. of patients with any grade 3/4 SAE				
No. of patients with any grade 4 SAE				
Any grade 3/4 treatment-related † SAE				
Any grade 4 treatment-related † SAE				
No. of patients with deaths associated with AEs				
No. of patients with deaths associated with treatment-related † AEs				
No. of patients with dose delays associated with AEs				
No. of patients with dose delays associated with treatment-related † AEs				
No. of patients with dose reductions associated with AEs				
No. of patients with dose reductions associated with treatment-related † AEs				

SOC/PT	S1			S2					
	T	R	R	S1	S2	T			
All grades									
Gr $\geq$ 3									
Gr $\geq$ 4									
N(%)									
...									
Part A+B (S1)									
SOC/PT	T			R			Total		
	All grades	Gr $\geq$ 3	Gr $\geq$ 4	All grades	Gr $\geq$ 3	Gr $\geq$ 4	All grades	Gr $\geq$ 3	Gr $\geq$ 4
N(%)									
...									

Notes: Percentage is based on number of patients by study part and sequence, when applicable.

† Related to both or lurbinectedin or itraconazole or with unknown relationship.

Part A, patients assigned to Sequence 1; Part B, sequence assigned randomly.

S1, Sequence 1; S2, Sequence 2.

T, Test (ITZ+LRB); R, Reference (LRB alone: NA).

Table 11.2.1.5 Treatment related† (or with unknown relationship) Adverse Events. Worst grade per patient

Part A												
SOC/PT	T			R			All grades N(%)	Gr ≥ 3 N(%)	Gr ≥ 4 N(%)			
	All grades N(%)	Gr ≥ 3 N(%)	Gr ≥ 4 N(%)	All grades N(%)	Gr ≥ 3 N(%)	Gr ≥ 4 N(%)						
	...											
Part B												
SOC/PT	S1			S2			All grades N(%)	Gr ≥ 3 N(%)	Gr ≥ 4 N(%)			
	T	R	R	S1	S2	T						
	All grades N(%)	Gr ≥ 3 N(%)	Gr ≥ 4 N(%)	All grades N(%)	Gr ≥ 3 N(%)	Gr ≥ 4 N(%)						
...												
Part A+B (S1)												
SOC/PT	T			R			Total					
	All grades N(%)	Gr ≥ 3 N(%)	Gr ≥ 4 N(%)	All grades N(%)	Gr ≥ 3 N(%)	Gr ≥ 4 N(%)	All grades N(%)	Gr ≥ 3 N(%)	Gr ≥ 4 N(%)			
	...											

Notes: Percentage is based on number of patients by study part and sequence, when applicable.

A supplementary Table 11.2.1.5supp will be created with grades 1,2,3,4,5.

† Related to both or lurbinectedin or itraconazole or with unknown relationship.

Part A, patients assigned to Sequence 1; Part B, sequence assigned randomly.

S1, Sequence 1; S2, Sequence 2.

T, Test (ITZ+LRB); R, Reference (LRB alone).

Table 11.2.1.6 Lurbinectedin related† Adverse Events. Worst grade per patient

SOC / PT	Part A				Part B				Part A+B				Total			
	S1 (TR)		S1 (TR)		S2 (RT)		S1 (TR)		S1 (TR)		S1 (TR)					
	All grades	Gr ≥ 3	Gr ≥ 4	All grades	Gr ≥ 3	Gr ≥ 4	All grades	Gr ≥ 3	Gr ≥ 4	All grades	Gr ≥ 3	Gr ≥ 4	All grades	Gr ≥ 3	Gr ≥ 4	
	N	%	N	%	N	%	N	%	N	%	N	%	N	%	N	%
...																

Notes: Percentage is based on number of patients by study part and sequence, when applicable.

† Related to both or lurbinectedin or with unknown relationship

Part A, patients assigned to Sequence 1; Part B, sequence assigned randomly.

S1, Sequence 1; S2, Sequence 2; TR, test-reference; RT, reference-test.

Table 11.2.1.7 Itraconazole related Adverse Events. Worst grade per patient

SOC / PT	Part A				Part B				Part A+B				Total			
	S1 (TR)		S1 (TR)		S2 (RT)		S1 (TR)		S1 (TR)		S1 (TR)					
	All grades	Gr ≥ 3	Gr ≥ 4	All grades	Gr ≥ 3	Gr ≥ 4	All grades	Gr ≥ 3	Gr ≥ 4	All grades	Gr ≥ 3	Gr ≥ 4	All grades	Gr ≥ 3	Gr ≥ 4	
	N	%	N	%	N	%	N	%	N	%	N	%	N	%	N	%
...																

Notes: Percentage is based on number of patients by study part and sequence, when applicable.

† Related to both or itraconazole or with unknown relationship

Part A, patients assigned to Sequence 1; Part B, sequence assigned randomly.

S1, Sequence 1; S2, Sequence 2; TR, test-reference; RT, reference-test.

Table 11.2.1.8 Adverse Events regardless of relationship. Worst grade by treatment

Part A										
SOC/PT	T			R						
	All grades		Gr $\geq$ 3	Gr $\geq$ 4	All grades		Gr $\geq$ 3	Gr $\geq$ 4		
	N(%)	N(%)	N(%)	N(%)	N(%)	N(%)	N(%)	N(%)	N(%)	N(%)
...										

Part B									
SOC/PT	S1			S2					
	T		R	R		T			
	All grades	Gr $\geq$ 3	Gr $\geq$ 4	All grades	Gr $\geq$ 3	Gr $\geq$ 4	All grades	Gr $\geq$ 3	Gr $\geq$ 4
...									

Part A+B (S1)											
SOC/PT	T			R			Total				
	All grades		Gr $\geq$ 3	Gr $\geq$ 4	All grades		Gr $\geq$ 3	Gr $\geq$ 4	All grades	Gr $\geq$ 3	Gr $\geq$ 4
	N(%)	N(%)	N(%)	N(%)	N(%)	N(%)	N(%)	N(%)	N(%)	N(%)	N(%)
...											

Notes: Percentage is based on number of patients by study part and sequence, when applicable.

† Related to both or lurbinectedin or itraconazole or with unknown relationship.

Part A, patients assigned to Sequence 1; Part B, sequence assigned randomly.

S1, Sequence 1; S2, Sequence 2.

T, Test (ITZ+LRB); R, Reference (LRB alone).

Table 11.2.1.9 Adverse Events regardless of relationship. Worst grade per patient

SOC / PT	Part A				Part B				Part A+B				Total			
	S1 (TR)				S1 (TR)				S2 (RT)							
	All grades	Gr ≥ 3	Gr ≥ 4	All grades	Gr ≥ 3	Gr ≥ 4	All grades	Gr ≥ 3	Gr ≥ 4	All grades	Gr ≥ 3	Gr ≥ 4	All grades	Gr ≥ 3	Gr ≥ 4	
	N	%	N	%	N	%	N	%	N	%	N	%	N	%	N	%
...																

Notes: Percentage is based on number of patients by study part and sequence, when applicable.

Part A, patients assigned to Sequence 1; Part B, sequence assigned randomly.

S1, Sequence 1; S2, Sequence 2; TR, test-reference; RT, reference-test.

**Listing 11.2.1.10 AEs grade ≥ 3**

Study	Sequence	Treatment	Subject	Cycle	Literal	SOC	PT	Grade	SAE	Start	End	Relationship	Action	Serious	Outcome
Part						term			(Y/N)	date	date	to study	taken	Event	medication
...															

Part A, patients assigned to Sequence 1; Part B, sequence assigned randomly.

\* ITZ+LRB / LRB

**Listing 11.2.1.11 AEs related only to lurbinectedin**

Study	Part	Sequence	Treatment	Subject	Cycle	Literal	SOC	PT	Grade	SAE	Start	End	Action	Serious	Outcome
							term			(Y/N)	date	date	taken	Event	
...															

Part A, patients assigned to Sequence 1; Part B, sequence assigned randomly.

\* ITZ+LRB / LRB

**Listing 11.2.1.12 AEs related only to itraconazole**

Study	Part	Sequence	Treatment	Subject	Cycle	Literal	SOC	PT	Grade	SAE	Start	End	Action	Serious	Outcome
							term			(Y/N)	date	date	taken	Event	
...															

Part A, patients assigned to Sequence 1; Part B, sequence assigned randomly.

\* ITZ+LRB / LRB

### 11.2.2 Evolution of Signs and Symptoms during the Treatment

Worst grade of signs and symptoms present at baseline and their evolution during treatment will be shown regardless of relationship.

Table 11.2.2.1 Shift of signs and symptoms during treatment

MedDRA PT	Baseline grade	Worst grade per patient during treatment									
		Grade 1		Grade 2		Grade 3		Grade 4		Grade 5	
		N	%	N	%	N	%	N	%	N	%
Part A - S1 (TR)											
...	1										
	2										
	...										
...	1										
	...										
Part B - S1 (TR)											
...	1										
	...										
...	1										
	...										
Part B - S2 (RT)											
...	1										
	...										
...	1										
	...										

Part A, patients assigned to Sequence 1; Part B, sequence assigned randomly.

S1, Sequence 1; S2, Sequence 2; TR, test-reference; RT, reference-test.

Test, ITZ+LRB; Reference, LRB alone.

## 11.3 Serious Adverse Events and Deaths

### 11.3.1 Serious Adverse Events

This analysis will be carried out on evaluable patients for the safety population.

All serious adverse events tables will be listed by study part and sequence and differentiating by treatment (Test, Reference or both). Additional groups could be done (such as PM01183 alone or in combination) if required, and a sequential number will be added at the end of the table number.

The type of toxicity and worst grade or severity by cycle and by patient will be summarized according to System Organ Class (SOC) and Preferred Term (PT) as per the MedDRA dictionary. Subsequent grouping of similar or clinically related items might be appropriate at the time of the analysis. Tables will be organized by category of events using SOC and PT. Grades could be presented by separate or any other grouping at the time of the analysis.

If the number of SAEs are very low, these tables will not be presented and only listings will be shown.

Table 11.3.1.1 Treatment related† (or with unknown relationship) SAEs. Worst grade by treatment

Part A												
SOC/PT	T			R			All grades	Gr ≥ 3	Gr ≥ 4			
	All grades	Gr ≥ 3	Gr ≥ 4	All grades	Gr ≥ 3	Gr ≥ 4						
...												
Part B												
SOC/PT	S1			S2			T	R	T			
	All grades	Gr ≥ 3	Gr ≥ 4	All grades	Gr ≥ 3	Gr ≥ 4						
...												
Part A+B (S1)												
SOC/PT	T			R			Total					
	All grades	Gr ≥ 3	Gr ≥ 4	All grades	Gr ≥ 3	Gr ≥ 4	All grades	Gr ≥ 3	Gr ≥ 4			
...												

Notes: Percentage is based on number of patients by study part and sequence, when applicable.

† Related to both or luteinizing hormone-releasing hormone (LHRH) agonist or with unknown relationship.

Part A, patients assigned to Sequence 1; Part B, sequence assigned randomly.

S1, Sequence 1; S2, Sequence 2.

T, Test (ITZ+LRB); R, Reference (LRB alone).

Table 11.3.1.2 Lurbinectedin related† SAEs. Worst grade by treatment

Notes: Percentage is based on number of patients by study part and sequence, when applicable.

† Related to both or lurbinectedin or itraconazole or with unknown relationship.

Part A, patients assigned to Sequence 1; Part B, sequence assigned randomly.

S1, Sequence 1; S2, Sequence 2.

T, Test (ITZ+LRB); R, Reference (LRB alone).

Table 11.3.1.3 Itraconazole related† SAEs. Worst grade by treatment

	N(%)								
--	------	------	------	------	------	------	------	------	------

...

Notes: Percentage is based on number of patients by study part and sequence, when applicable.

† Related to both or lurbinectedin or itraconazole or with unknown relationship.

Part A, patients assigned to Sequence 1; Part B, sequence assigned randomly.

S1, Sequence 1; S2, Sequence 2.

T, Test (ITZ+LRB); R, Reference (LRB alone).

Table 11.3.1.4 Treatment related† (or with unknown relationship) SAEs. Worst grade per patient

SOC / PT	Part A				Part B				Part A+B				Total	
	S1 (TR)		S1 (TR)		S2 (RT)		S1 (TR)		S1 (TR)		S1 (TR)			
	All grades	Gr ≥ 3	Gr ≥ 4	All grades	Gr ≥ 3	Gr ≥ 4	All grades	Gr ≥ 3	Gr ≥ 4	All grades	Gr ≥ 3	Gr ≥ 4		
	N	%	N	N	%	N	%	N	%	N	%	N	%	
...														

Notes: Percentage is based on number of patients by study part and sequence, when applicable.

† Related to both or lurbinectedin or itraconazole or with unknown relationship

Part A, patients assigned to Sequence 1; Part B, sequence assigned randomly.

S1, Sequence 1; S2, Sequence 2; TR, test-reference; RT, reference-test.

Table 11.3.1.5 Lurbinectedin related† SAEs. Worst grade per patient

SOC / PT	Part A				Part B				Part A+B				Total	
	S1 (TR)		S1 (TR)		S2 (RT)		S1 (TR)		S1 (TR)		S1 (TR)			
	All grades	Gr ≥ 3	Gr ≥ 4	All grades	Gr ≥ 3	Gr ≥ 4	All grades	Gr ≥ 3	Gr ≥ 4	All grades	Gr ≥ 3	Gr ≥ 4		
	N	%	N	N	%	N	%	N	%	N	%	N	%	
...														

Notes: Percentage is based on number of patients by study part and sequence, when applicable.

† Related to both or lurbinectedin or with unknown relationship

Part A, patients assigned to Sequence 1; Part B, sequence assigned randomly.

S1, Sequence 1; S2, Sequence 2; TR, test-reference; RT, reference-test.

Table 11.3.1.6 Itraconazole related SAEs. Worst grade per patient

SOC / PT	Part A				Part B				Part A+B				Total	
	S1 (TR)		S1 (TR)		S2 (RT)		S1 (TR)		S1 (TR)		S1 (TR)			
	All grades	Gr ≥ 3	Gr ≥ 4	All grades	Gr ≥ 3	Gr ≥ 4	All grades	Gr ≥ 3	Gr ≥ 4	All grades	Gr ≥ 3	Gr ≥ 4		
	N	%	N	N	%	N	%	N	%	N	%	N	%	
...														

Notes: Percentage is based on number of patients by study part and sequence, when applicable.

† Related to both or itraconazole or with unknown relationship

Part A, patients assigned to Sequence 1; Part B, sequence assigned randomly.

S1, Sequence 1; S2, Sequence 2; TR, test-reference; RT, reference-test.

T, Test (ITZ+LRB); R, Reference (LRB alone: NA).

Table 11.3.1.7 SAEs regardless of relationship. Worst grade by treatment

Part A											
SOC/PT	T			R							
	All grades		Gr ≥ 3	Gr ≥ 4	All grades		Gr ≥ 3	Gr ≥ 4			
	N(%)	N(%)	N(%)	N(%)	N(%)	N(%)	N(%)	N(%)	N(%)	N(%)	N(%)
...											
Part B											
SOC/PT	S1			S2							
	T		R		R		T				
	All grades	Gr ≥ 3	Gr ≥ 4	All grades	Gr ≥ 3	Gr ≥ 4	All grades	Gr ≥ 3	Gr ≥ 4	All grades	Gr ≥ 3
N(%)											
...											
Part A+B (S1)											
SOC/PT	T			R			Total				
	All grades	Gr ≥ 3	Gr ≥ 4	All grades	Gr ≥ 3	Gr ≥ 4	All grades	Gr ≥ 3	Gr ≥ 4	All grades	Gr ≥ 3
N(%)											
...											

Notes: Percentage is based on number of patients by study part and sequence, when applicable.

† Related to both or luteinizing hormone-releasing hormone (LHRH) agonist or with unknown relationship.

Part A, patients assigned to Sequence 1; Part B, sequence assigned randomly.

S1, Sequence 1; S2, Sequence 2.

T, Test (ITZ+LRB); R, Reference (LRB alone).

Table 11.3.1.8 SAEs regardless of relationship. Worst grade per patient

SOC / PT	Part A			Part B			Part A+B			Total		
	S1 (TR)			S1 (TR)			S2 (RT)			S1 (TR)		
	All grades	Gr ≥ 3	Gr ≥ 4	All grades	Gr ≥ 3	Gr ≥ 4	All grades	Gr ≥ 3	Gr ≥ 4	All grades	Gr ≥ 3	Gr ≥ 4
	N %	N %	N %	N %	N %	N %	N %	N %	N %	N %	N %	N %
...												

Notes: Percentage is based on number of patients by study part and sequence, when applicable.

Part A, patients assigned to Sequence 1; Part B, sequence assigned randomly.

S1, Sequence 1; S2, Sequence 2; TR, test-reference; RT, reference-test.

#### Listing 11.3.1.9 All SAEs†

Study Part	Sequence Group*	Treatment Group*	Subject	SOC	PT	Grade	AE Status	AE Relationship	AE consequences	Start date	End date

† SAE narratives will be provided by the pharmacovigilance department

\* ITZ+LRB / LRB

### 11.3.2 Deaths

Table 11.3.2.1 Cause of death

	Part A		Part B		Part A+B		Total	
	S1 (TR)		S1 (TR)		S2 (RT)		S1 (TR)	
	N	%	N	%	N	%	N	%
Malignant disease								
Adverse Event(s)								
Other ‡								
Total								

Notes: Percentage is based on number of patients who died by study part and sequence, when applicable.

‡ Specify.

Part A, patients assigned to Sequence 1; Part B, sequence assigned randomly.

S1, Sequence 1; S2, Sequence 2; TR, test-reference; RT, reference-test.

Listing 11.3.2.2 Deaths

Study Part	Sequence Group*	Treatment	Subject	Cycle	Death date	Cause of death	No. of cycles administered	Time on treatment †	Time from first dose (days)	Time from last dose (days)
...										

\* ITZ+LRB / LRB

## 11.4 Clinical Laboratory Evaluation

Tables will be listed by study part and sequence, however, additional groups could be done (such as PM01183 alone or in combination) if required, and a sequential number will be added at the end of the table number.

Grades could be presented by separate or any other grouping at the time of the analysis.

### 11.4.1 Hematological Abnormalities

Table 11.4.1.1 Hematological abnormalities: Worst grade by treatment

Part A											
SOC/PT	T			R							
	All grades		Gr $\geq$ 3	Gr $\geq$ 4	All grades		Gr $\geq$ 3	Gr $\geq$ 4			
	N(%)	N(%)	N(%)	N(%)	N(%)	N(%)	N(%)	N(%)	N(%)	N(%)	
Anemia											
Leukopenia											
Lymphopenia											
Neutropenia											
Thrombocytopenia											
Part B											
SOC/PT	S1				S2						
	T		R		R		T				
	All grades	Gr $\geq$ 3	Gr $\geq$ 4	All grades	Gr $\geq$ 3	Gr $\geq$ 4	All grades	Gr $\geq$ 3	All grades	Gr $\geq$ 3	Gr $\geq$ 4
Anemia											
Leukopenia											
Lymphopenia											
Neutropenia											
Thrombocytopenia											
Part A+B (S1)										Total	
SOC/PT	T			R						Total	
	All grades	Gr $\geq$ 3	Gr $\geq$ 4	All grades	Gr $\geq$ 3	Gr $\geq$ 4	All grades	Gr $\geq$ 3	Gr $\geq$ 4	Total	
	N(%)	N(%)	N(%)	N(%)	N(%)	N(%)	N(%)	N(%)	N(%)	N(%)	
Anemia											
Leukopenia											
Lymphopenia											
Neutropenia											
Thrombocytopenia											

Notes: Percentage is based on number of patients by study part and sequence, when applicable.

† Related to both or lurbinectedin or itraconazole or with unknown relationship.

Part A, patients assigned to Sequence 1; Part B, sequence assigned randomly.

S1, Sequence 1; S2, Sequence 2.

T, Test (ITZ+LRB); R, Reference (LRB alone).

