after 2 days of delay the patient does not meet the criteria for treatment continuation, itraconazole will be stopped and the patient will be considered not evaluable for the trial.

If the criteria for treatment continuation are not met as described above, treatment must be discontinued and the EOT visit performed.

**Table 7.** Criteria for lorbinecetin treatment continuation.

Variable	Lorbinecetin (Day 1)
ECOG PS	$\leq 1$
ANC	$\geq 1.5 \times 10^9/L$
Platelets	$\geq 100 \times 10^9/L$
Hemoglobin a	$\geq 8.0 \text{ g/dL}$
Total bilirubin	$\leq 1.0 \times \text{ULN}$ . If it is $> 1.0 \times \text{ULN}$ but $\leq 1.5 \times \text{ULN}$ , direct bilirubin must be $\leq 1.0 \times \text{ULN}$
Albumin	$\geq 3.0 \text{ g/dL}$
AST/ALT	$\leq 3.0 \times \text{ULN}$
CPK	$\leq 2.5 \times \text{ULN}$ ( $\leq 5.0 \times \text{ULN}$ is acceptable if elevation is disease-related)
Serum Creatinine levels/ Calculated CLcr (Cockcroft and Gault's formula)	Serum creatinine levels $\leq \text{ULN}$ or calculated CLcr $\geq 30 \text{ mL/min}$ , if abnormal ( $>\text{ULN}$ ) serum creatinine levels
Other non-hematological drug-related AEs (except increased AP, or grade 2 alopecia, asthenia, and non-optimally treated nausea and/or vomiting) b	Grade $\leq 1$

a Patients may receive PRBC transfusions and/or EPO treatment if clinically indicated to increase/maintain adequate hemoglobin levels.

b Any grade allowed for increased GGT and up to grade 2 allowed for neuropathy.

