### 6.1 *Toxicity and Adverse Events*

Treatment-emergent adverse events (TEAEs) are any adverse event aggravated in severity from baseline or having their onset between the first dose of the study drug and 31-day ( $\pm 10$  days) after the last treatment dose, death or date of further therapy, whichever came first. AEs related to the study treatment or with unknown relationship occurring more than 31 days after the last dose were also taken into account as TEAEs.

Summary of overall AEs will be done by system organ class (SOC) and preferred term (PT), by severity (worst toxicity grade) and by relationship to the study drug (any of them or both). Tables will be sorted by category of events using SOC (i.e. alphabetic order) and PT in descending frequencies (i.e. from higher to lower).

AEs, SAEs, deaths, laboratory evaluations, dose delays/omissions/reductions and study drug discontinuations due to AEs will be tabulated in a descriptive way. Counts and percentages will be used for categorical variables, and summary tables will be used for continuous variables.

Patients having any treatment-related grade  $\geq 3$  AEs should have relevant tests reassessed at least every 72 hours until recovery to at least grade 2.

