### 6.2 *Clinical Laboratory Evaluation*

Laboratory results will be classified according to the NCI-CTCAE v.5. All laboratory visits reported as “End of treatment” visit will be mapped to the last cycle visit for each patient.

The following hematological values will be displayed: white blood cells count (WBC), neutrophil count, lymphocyte count, monocyte count, erythrocytes, hemoglobin, hematocrit and platelet count. Worst grade per patient and per cycle for anaemia, lymphopenia, neutropenia, leukopenia and thrombocytopenia during treatment will be shown.

Overall cross tabulation will be presented for the worst grade during treatment vs. the baseline toxicity grading of anaemia, lymphopenia, neutropenia, leukopenia and thrombocytopenia.

If a grade 3/4 neutropenia or thrombocytopenia increase occurs during a treatment cycle, the first day the onset value is reached (counting from the start of the cycle) will be tabulated. Time to recovery of the abnormality (i.e., grade 3/4 neutropenia or thrombocytopenia) will be assessed and defined as the time, in days, from the start of the grade 3/4 abnormality until the abnormality is recovered (grade  $\leq 2$ ). The analysis will be carried out taking into account all events, including those that occur in a same cycle. The information will be shown by means of median and range.

Likewise, the following biochemical and coagulation values will be displayed: aspartate aminotransferase (AST), alanine aminotransferase (ALT), lactate dehydrogenase (LDH), creatinine, creatinine clearance, glucose, creatine phosphokinase (CPK), CPK-MB fraction, gamma glutamyltransferase (GGT), total bilirubin, direct bilirubin, serum electrolytes (Na+, K+, Mg++, Ca++), total proteins, albumin, C-reactive protein count (CRP) and the international normalized ratio (INR). Worst grade per patient and per cycle for applicable values during treatment will be shown.

Time to recovery of the abnormality (grade 3/4 AST or ALT) will be assessed and defined as the time, in days, from the start of the grade 3/4 abnormality until recovery to grade  $\leq 2$ . The analysis will be carried out taking into account all events, including those that occur in a same cycle. The information will be shown by means of median and range.

Overall cross tabulation will be presented for the worst grade during treatment vs. the baseline toxicity grading of biochemical abnormalities.

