## **7.3 Baseline and Demographic Data**

Baseline data such as demographics, cancer history, prior therapy, prior relevant history, signs and symptoms, electrocardiogram, LVEF, physical examination, vital signs, laboratory values and concomitant medication, coded according to the World Health Organization (WHO) Anatomical Therapeutic Chemical (ATC) classification system, will be described following standard tables detailed in Appendix I.

Age, baseline weight, height and BSA values will be summarized descriptively. Age categories, sex, race and baseline ECOG PS score will be summarized with frequency counts.

For the cancer history, time from initial diagnosis, time from metastatic disease, time from locally advanced disease and time from last progression before the study entry will be summarized. This time calculations will be shown in months and summarized descriptively. Tumor type and other characteristics of the primary and current disease will be described using standard tables detailed in Appendix I.

Previous relevant medical history (other than cancer) will be listed.

A frequency tabulation of the number of patients with the different types of previous surgery, radiotherapy or therapy (number of lines) will be given.

Signs and symptoms will be displayed by tabulation of frequencies according to NCI-CTCAE v.5 toxicity grades. Signs and symptoms will be listed.

In case of pre-treatment characteristics with multiple measurements per subject before the start of treatment (e.g. laboratory assessments or vital signs), the last value prior to or on the first day of treatment will be considered the baseline measurement.

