## 11.4.2 Biochemical Abnormalities

Table 11.4.2.1 Biochemical abnormalities: Worst grade per treatment

Part A																			
T			R																
All grades		Gr ≥ 3	Gr ≥ 4		All grades		Gr ≥ 3	Gr ≥ 4		All grades									
N(%)		N(%)	N(%)		N(%)		N(%)	N(%)		N(%)									
ALT increase																			
AST increase																			
...*																			
Part B																			
S1						S2													
T			R			R			T										
All grades		Gr ≥ 3	Gr ≥ 4	All grades		Gr ≥ 3	Gr ≥ 4	All grades		Gr ≥ 3	Gr ≥ 4								
N(%)		N(%)	N(%)	N(%)		N(%)	N(%)	N(%)		N(%)	N(%)								
ALT increase																			
AST increase																			
...*																			
Part A+B (S1)																			
T						R													
All grades		Gr ≥ 3	Gr ≥ 4	All grades		Gr ≥ 3	Gr ≥ 4	All grades		Gr ≥ 3	Gr ≥ 4								
N(%)		N(%)	N(%)	N(%)		N(%)	N(%)	N(%)		N(%)	N(%)								
ALT increase																			
AST increase																			
...*																			

Notes: Percentage is based on number of patients by study part and sequence, when applicable.

\*Creatinine increased, hyperglycemia, hypoglycemia, CPK increased, GGT increased, bilirubin increased, hypoalbuminemia, hypernatremia, hyponatremia, hyperkalemia, hypokalemia, hypermagnesemia, hypomagnesemia, hypercalcemia, hypocalcemia.

Part A, patients assigned to Sequence 1; Part B, sequence assigned randomly.

S1, Sequence 1; S2, Sequence 2.

T, Test (ITZ+LRB); R, Reference (LRB alone).

Listing 11.4.2.2 Biochemical abnormalities grade ≥ 3 by treatment

Study Part	Sequence	Treatment Group*	Subject	Event	Grade
...					

\* ITZ+LRB / LRB

Listing 11.4.2.3 Biochemical tests not assessed by treatment

Study Part	Sequence	Treatment Group*	Subject	Lab. test
...				

\* ITZ+LRB / LRB

Table 11.4.2.4 Biochemical abnormalities: Worst grade per patientpatientpatientpatientpatient

	Part A						Part B						Part A+B						Total	
	S1 (TR)			S1 (TR)			S2 (RT)			S1 (TR)			S1 (TR)			S1 (TR)				
	All grades	Gr ≥ 3	Gr ≥ 4	All grades	Gr ≥ 3	Gr ≥ 4	All grades	Gr ≥ 3	Gr ≥ 4	All grades	Gr ≥ 3	Gr ≥ 4	All grades	Gr ≥ 3	Gr ≥ 4	All grades	Gr ≥ 3	Gr ≥ 4		
	N	%	N	%	N	%	N	%	N	%	N	%	N	%	N	%	N	%		
ALT increase																				
AST increase																				
...	*																			

Notes: Percentage is based on number of patients by study part and sequence, when applicable.

Part A, patients assigned to Sequence 1; Part B, sequence assigned randomly.

S1, Sequence 1; S2, Sequence 2; TR, test-reference; RT, reference-test.

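### The by-treatment laboratory tables ignore the grade a patient held when each cycle began, so abnormalities present at entry or persisting from the previous cycle count under both Test and Reference

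*SAP*

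**What the plan says.** - **Counting rule.** SAP 6.2 states for hematology: "Worst grade per patient and per cycle for anaemia, lymphopenia, neutropenia, leukopenia and thrombocytopenia during treatment will be shown". For biochemistry it states: "Worst grade per patient and per cycle for applicable values during treatment will be shown". Tables 11.4.1.1 ("Hematological abnormalities: Worst grade by treatment") and 11.4.2.1 ("Biochemical abnormalities: Worst grade per treatment") place these grades under T or R, in All-grades, grade 3 or higher and grade 4 or higher columns. Part B is split by sequence. The pooled Part A+B columns for T and R use Sequence 1 only.
- **Emergence.** SAP 6.1 defines treatment-emergent events as "any adverse event aggravated in severity from baseline or having their onset between the first dose of the study drug" and the end of follow-up. That definition covers adverse events, not laboratory grades.
- **Baseline.** SAP 7.3 sets one baseline for the study: "the last value prior to or on the first day of treatment will be considered the baseline measurement". There is no baseline for Cycle 2 or Cycle 3.
- **Baseline-referenced laboratory output.** Shift Tables 11.4.3.1 and 11.4.3.3 use the worst grade over the whole treatment, by part and sequence. They do not separate T from R.
- **Role of the tables.** SAP 11.2 warns that laboratory abnormalities may be under-reported as adverse events and sends the reader to Section 11.4.
- **Formal comparison.** Table 11.5.1.1 has grade 3-4 and grade 4 laboratory rows. They come from a mixed model with treatment, period and sequence, to be fitted if applicable.
- **Re-treatment criteria.** Protocol 7.4, Table 7, allows a new cycle with hemoglobin down to 8.0 g/dL, AST/ALT up to 3.0 x ULN and albumin down to 3.0 g/dL. It sets no limit for lymphocytes or leukocytes.

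**The concern.** The effect of itraconazole on lurbinectedin's safety profile is a secondary objective, and myelosuppression is the drug's most relevant toxicity. The T and R laboratory columns are where a reader will look for that effect. They mix two things: abnormalities that arose under the treatment named in the column, and abnormalities the patient brought into the cycle. Entry abnormalities count on both sides and dilute the contrast. Abnormalities persisting from the previous cycle are charged to whichever treatment comes second.

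Two features add to this. The SAP does not say which cycle a pre-infusion Day 1 sample belongs to, and the calculated cycle in its listings is undefined. In the protocol's Schedule of Assessments, Biochemistry-B (electrolytes, albumin) is drawn only at screening, on Day 1 of each cycle and at end of treatment. If samples follow the visit label, the Cycle 2 Day 1 value, which reflects Cycle 1, is scored to Cycle 2's treatment. Optional Cycle 3 is lurbinectedin alone, so in Sequence 2 a Test abnormality can be scored once more under Reference.

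**Working it through.** The plan states no figure to reproduce. The text settles whether double counting occurs; the arithmetic only shows how it behaves.

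**Inputs from the documents.** Part A has 3 patients, all TR. Part B has 8 randomized 1:1, taken as 4 TR and 4 RT. That gives 3 + 4 = 7 TR and 4 RT. Planned lurbinectedin doses are 0.8 mg/m² in Test and 3.2 mg/m² in Reference. Protocol 3.2 does not expect exposure in Test to exceed that in Reference.

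**Assumed inputs.** b = prevalence at entry; q = chance that a Cycle 1 abnormality is still seen in Cycle 2; e1, e2 = new-onset risks under the treatments of Cycles 1 and 2.

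**Formulas.** Printed in Cycle 1: C1 = b + (1 − b) × e1. Printed in Cycle 2: C2 = q × C1 + (1 − q × C1) × e2.

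**Reference more toxic** (Test 0.20, Reference 0.60, b = 0, q = 0.5):
- Sequence 1: Test 0.20; Reference 0.10 + 0.90 × 0.60 = 0.64. The difference widens from −0.40 to −0.44.
- Sequence 2: Reference 0.60; Test 0.30 + 0.70 × 0.20 = 0.44. The difference shrinks to −0.16.
- Excess in patients: Sequence 2 Test, 4 × 0.24 = 0.96; Sequence 1 Reference, 7 × 0.04 = 0.28.
- All 11 patients: Test (7 × 0.20 + 4 × 0.44)/11 = 0.29; Reference (7 × 0.64 + 4 × 0.60)/11 = 0.63; difference −0.34. Part B alone: 0.32 − 0.62 = −0.30.

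**Other cases with the same risks.** The true difference is −0.40 throughout.

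| b | q | 11 patients | Part B alone |
|---|---|---|---|
| 0 | 0.5 | −0.34 | −0.30 |
| 0 | 1 | −0.28 | −0.20 |
| 0.3 | 1 | −0.19 | −0.14 |
| 0.6 | 1 | −0.11 | −0.08 |

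**Equal risks** (both 0.20, b = 0, q = 1). Sequence 1 prints Test 0.20 and Reference 0.36. Sequence 2 prints Reference 0.20 and Test 0.36. This cancels in Part B, but over 7 and 4 patients it leaves (7 × 0.20 + 4 × 0.36)/11 − (7 × 0.36 + 4 × 0.20)/11 = −0.04.

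**The period term.** In the first case carry-over adds 0.04 to Cycle 2 in Sequence 1 and 0.24 in Sequence 2. A single period effect cannot absorb amounts that differ by preceding treatment.

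**The denominator.** In Sequence 2 Test, new events are 0.70 × 0.20 = 0.14. Divided by all patients this is 14%, which is too low. Divided by the 0.70 still at risk it is 20%, the assumed risk.

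**The case against.** The case against has substance. The laboratory analysis is descriptive, with no decision rule attached. About 11 patients are planned, and listings by treatment plus dated values let a reader trace carry-over case by case. Part B is printed by sequence, so order is visible. SAP 11.4 permits further groupings, and SAP 7.12 defers conventions to a separate document. All of this limits the harm. None of it supplies a counting rule, and the tables as specified still count persisting abnormalities twice.

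Three stronger readings are tempting but not supported:
- *Reference inherits Test toxicity in Sequence 1, so the contrast shrinks or reverses.* This needs Test to be the more toxic cycle. With 40% against 20% and q = 0.5, Reference would print 0.20 + 0.80 × 0.40 × 0.5 = 0.36. The planned doses and Protocol 3.2 do not predict that, and in the case worked above the Sequence 1 contrast widens. Because the Part B dose may be adjusted towards comparable AUC, the direction is not fixed in advance.
- *Severe cytopenias are carried over freely.* Table 7 requires ANC of at least 1.5, platelets of at least 100 (both × 10⁹/L) and hemoglobin of at least 8.0 g/dL on Day 1. That keeps most unresolved grade 3 or higher neutropenia, thrombocytopenia and anemia out of the next cycle, assuming the grade 3 cut-offs lie at or below those limits; the documents do not state them.
- *Chemistry has no limits, and GGT may be any grade.* Table 7 limits bilirubin, albumin, AST/ALT, CPK and creatinine or its clearance. Its row for other non-hematological drug-related events can also catch glucose or electrolyte changes reported as such. Footnote b to Table 7 says "Any grade allowed for increased GGT and up to grade 2 allowed for neuropathy", but the matching synopsis footnote (Table S2) names alkaline phosphatase. The two must be reconciled; this point does not depend on either.

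**Conclusion.** The concern holds as a gap in the counting rule. Tables 11.4.1.1 and 11.4.2.1, and the laboratory rows of Table 11.5.1.1 if that model is run, score any abnormality seen in a cycle against that cycle's treatment, whatever the grade at its start. The All-grades columns are affected most, then the grade 3 or higher columns for tests without a specific Table 7 limit, such as lymphocytes and leukocytes. At the planned doses the main distortion is an inflated Test column in Sequence 2, and it does not cancel over about 7 TR and 4 RT patients. Under the assumed risks of 20% and 60%, a 40-point difference prints as 34 to 11 points, depending on persistence and prevalence at entry. Those sizes rest wholly on assumed rates and on persistence and new onset being independent. The 11-patient figures describe pooling both sequences, which Table 11.4.1.1 does not itself do for T and R. The primary pharmacokinetic analysis is untouched.

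**What to change.** Keep the worst-grade tables and add the following:
- For each treatment (T/R), a shift table or a count of new or worsened grades against the pre-infusion Day 1 grade of that same cycle.
- A rule that the pre-infusion Day 1 sample belongs to the period before that cycle's infusion and is not on-cycle toxicity.
- A separate column for abnormalities already present at that sample, with the number of patients still at risk as denominator for each grade column.
- The same new-or-worsened definition for the laboratory rows of Table 11.5.1.1, at least as a sensitivity analysis.

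The last value before itraconazole may look like the cleaner reference, but it does not work well in Sequence 2. The Schedule has no Day 15 Biochemistry-B draw (Protocol Table 5 is looser), so the last pre-itraconazole value could be Cycle 1 Day 1. Day 15 blood counts also lie close to the nadir, which the protocol places in the middle of the second week.

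The cost is SAP wording and programming; no new samples are needed. There is one small downside: changes arising during the four-day itraconazole lead-in fall into the Test cycle's Day 1 reference. List any change from the last pre-itraconazole value where one exists.
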